#### **9.3.2.2.3.1.7. Cardiorespiratory Disorders**

An increased frequency of cardiorespiratory arrest or sudden death was observed with necitumumab. Cardiorespiratory arrest or sudden death was reported in the pivotal Study JFCC (SQUIRE) in 2.8% (15/538) of patients treated with necitumumab plus gemcitabine and cisplatin compared to 0.6% (3/541) of patients treated with chemotherapy alone. Twelve of the 15 patients died within 30 days of the last dose of necitumumab and had comorbid conditions, including history of chronic obstructive pulmonary disease (n=7), hypertension (n=5), hypomagnesemia (n=4), and coronary artery disease (n=3). Eleven of the 12 patients had an unwitnessed death.

### 12.1. Determination of Sample Size

A total of approximately 68 patients evaluable for either the Part A or Part B portions of the study will be enrolled. Part A requires up to 18 treated patients (3-6 per dosage cohort). Patients with squamous and nonsquamous NSCLC who received the recommended abemaciclib dose for Part B in Part A will also be part of the Part B portion of the trial. These patients will also be included in the interim ~~safety analysis analyses~~ as described in Section 12.2.10.

The final analysis of the study will take place approximately 5 months after the last patient evaluable for Part B portion of the study has been enrolled. The primary Part B outcome variable in this study will be the 3-month PFS rate. The Part B statistical null hypothesis states that the true 3-month PFS rate is 50%, whereas the research hypothesis states that the true 3-month PFS rate is 65%. Assuming the Part B portion of the study continues to a full enrollment of 50 evaluable patients, the null hypothesis will be rejected at the final analysis only if at least 60% of evaluable patients ~~experience~~experience PFS  $\geq 3$  months.

#### 12.2.10. Interim Analyses

~~A~~ safety interim analysis will be performed after the first 15 evaluable patients in the Part B portion of the trial have completed 2 cycles of study treatment (or otherwise discontinued study treatment). ~~Patients with squamous and nonsquamous NSCLC who received the recommended abemaciclib dose for Part B in Part A will be taken into account for the safety interim analysis.~~

The safety interim analysis will be conducted to permit evaluation of safety data by Lilly.

The results from the safety interim ~~analyses~~analysis will be examined by an internal assessment committee, which will be established prior to enrollment of the first patient in the trial. The internal assessment committee will consist of a Lilly medical director, a Lilly CRP/clinical research scientist, a PK scientist, and a statistician and will make recommendations about the trial. Enrollment will continue while the safety interim analysis is being performed. ~~Interim-~~The safety interim analysis results (including all tables, figures, and listings) will not be disseminated outside of the assessment committee, unless emerging safety outcomes warrant such a disclosure. In case a disclosure is warranted, the outcome of the safety interim

analyses-analysis will be documented, and a written letter will be submitted to the ERB(s) and the investigators for documentation purposes.

Interim analyses for efficacy may be performed as needed to aid in the planning of future trials. There is no plan to stop the study for positive efficacy. The type-1 error for final primary analysis will not be affected and hence is not adjusted.

Patients with squamous and nonsquamous NSCLC who received the recommended abemaciclib dose for Part B in Part A will be taken into account for the interim analyses.

## Attachment 2. Protocol JFCU Clinical Laboratory Tests

**Hematologya:**

Hemoglobin  
 Hematocrit  
 Erythrocyte count (RBC)  
 Mean cell volume (MCV)  
 Mean cell hemoglobin concentration (MCHC)  
 Leukocytes (WBC)  
 Neutrophils, segmented and bands  
 Lymphocytes  
 Monocytes  
 Eosinophils  
 Basophils  
 Platelets

**Urinalysisc**

Color  
 Specific gravity  
 pH  
 Protein  
 Glucose  
 Ketones  
 Blood  
 Urine leukocyte esterase

**Clinical Chemistrya:****Serum concentrations of:**

Sodium  
 Magnesium  
 Potassium  
Phosphate  
 Total bilirubin  
 Direct bilirubin  
 Alkaline phosphatase  
 Alanine aminotransferase (ALT)  
 Aspartate aminotransferase (AST)  
 Blood urea nitrogen (BUN)  
 Creatinineb  
 Uric acid  
 Calcium  
 Glucose, nonfasting  
 Albumin  
 Cholesterol  
 Creatine kinase (CK)

**Pregnancy Test** (females of childbearing potential only, serum required)d

**Coagulation Testsd:**

INR and PT  
 PTT  
 Fibrin D dimer  
 Protein C activity (baseline only)  
 Protein S activity (baseline only)

**Attachment 8. Protocol JFCU Inducers and Strong Inhibitors of CYP3A4 or Substrates of CYP2B**

**Substrates of CYP2B6**

Alfentanil  
Bupropion  
cyclophosphamide  
Efavirenz  
Ifosfamide  
methadone  
Nevirapine  
Propofol  
Sertraline  
sorafenib  
tamoxifen  
Valproic acid

4.1. Primary Objective

This study is divided into 2 parts:

Part A: to determine the dose-limiting toxicity (DLT) of abemaciclib at doses up to 200 mg when combined with necitumumab 800 mg, in patients with Stage IV non-small cell lung cancer (NSCLC) as measured by the number of patients with a DLT in Cycle 1.

Part B: to evaluate the efficacy of necitumumab in combination with abemaciclib in terms of progression-free survival (PFS) rate at 3 months in patients with Stage IV NSCLC.

4.2. Secondary Objectives

The secondary objectives of the study are as follows:

Part A:

- to investigate the safety profile as assessed by clinical and laboratory significant events of necitumumab in combination with abemaciclib
- to determine the overall response rate (ORR)
- to determine pharmacokinetics (PK) of necitumumab and abemaciclib
- to determine the immunogenicity of necitumumab

Part B:

To demonstrate the safety, efficacy, and feasibility of necitumumab in combination with abemaciclib at the recommended dose by:

- determining PFS
- determining ORR and disease control rate (DCR)
- estimating overall survival (OS)
- investigating the safety profile as assessed by clinical and laboratory significant events
- determining PK of necitumumab and abemaciclib
- determining the immunogenicity of necitumumab

The exploratory objectives of the study are to correlate biomarkers with clinical outcomes, including, but not limited to *KRAS* mutation assessment, epidermal growth factor receptor (EGFR) protein expression, and/or other biomarkers associated with the disease pathobiology, the cell cycle, EGFR pathway, and/or the mechanism of action of the therapeutic molecules. The biomarker-based analyses will be described in a separate Translational Research Statistical Analysis Plan.

5. A Priori Statistical Methods

5.1. Determination of Sample Size

A total of approximately 68 patients evaluable for either the Part A or Part B portions of the study will be enrolled. Part A requires up to 18 treated patients (3 to 6 per dosage cohort). Patients with squamous and nonsquamous NSCLC who received the recommended abemaciclib dose for Part B in Part A will also be part of the Part B portion of the trial. These patients will also be included in the interim safety analysis as described in Section 5.10.

An evaluable patient for Part B will include any patient enrolled in Part A and treated at the recommended doses of necitumumab and abemaciclib. In addition, patients will be entered strictly to Part B (with a total of 50 evaluable patients in Part B). To be evaluable for Part B of the study, these additional patients entered must meet the following criteria:

- The patient has received at least 1 dose each of necitumumab and abemaciclib.
- The patient has a complete radiographic assessment at baseline.

The final analysis of the study will take place approximately 5 months after the last patient evaluable for Part B portion of the study has been enrolled. The primary Part B outcome variable in this study will be the 3-month PFS rate. The Part B statistical null hypothesis states that the true 3-month PFS rate is 50%, whereas the research hypothesis states that the true 3-month PFS rate is 65%. Assuming the Part B portion of the study continues to a full enrollment of 50 evaluable patients, the null hypothesis will be rejected at the final analysis only if at least 60% of evaluable patients experience PFS ≥ 3 months.

If the research hypothesis is true, there is an 81% chance of reaching full Part B enrollment and rejecting the null hypothesis. If the null hypothesis is true, then there is a 10% chance of reaching full Part B enrollment and rejecting the null hypothesis. Therefore, the Part B portion of this study has a one-sided alpha level of 0.10, with statistical power of 81%.

5.2. General Considerations

The following populations will be defined for this study:

- **All enrolled population:** anyone who signed the informed consent will be included in this population.
- **Safety population:** all patients who have received any amount of study drug [necitumumab, and/or abemaciclib]
- **Evaluable population:** all patients who have received at least 1 dose each of necitumumab and abemaciclib and have had a complete radiographic assessment at baseline

Unless otherwise specified, for continuous variables, summary statistics will include number of patients, mean, median, standard deviation, minimum, and maximum. Categorical variables will be summarized using frequency and percentages.

- **Age (years):** $(\text{Informed Consent Date} - \text{Date of Birth} + 1)/365.25$, if only year of birth is collected, see Section 5.3 for date imputation.
- **Missing Data:** All analyses and descriptive summaries will be based on the observed data. Unless otherwise specified, missing data will not be imputed or “carried forward.”
- **Baseline Measurement:** Unless otherwise specified, the last nonmissing measurement prior to the first dose of study drug will serve as the baseline measurement.
- **Study Day:** Study day is calculated as assessment date – first dose date + 1 day if the assessment is done on or after the first dose day. If the assessment is done prior to the first dose day, study day will be calculated as assessment date – first dose date. Date of first dose is defined as study day 1.
- **Duration:** Duration is calculated as:
 - Duration (days): $(\text{End Date} - \text{Start Date} + 1)$
 - Duration (weeks): $(\text{End Date} - \text{Start Date} + 1)/7$
 - Duration (months): $(\text{End Date} - \text{Start Date} + 1)/30.4375$ (Days in months = $(1/12) \times \text{average number of days in a year.}$)
 - Duration (years): $(\text{End Date} - \text{Start Date} + 1)/365.25$ (Average days in a year = 365.25, reflecting the Julian Year of 3 years with 365 days each and one leap year of 366 days.)
- **Time-to-event:** The event or censoring time (days) is calculated as:
Date of event/censoring – Date of first dose of study drug + 1

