### 12.2. Statistical and Analytical Plans

#### 12.2.1. General Considerations

The primary analysis will be as described in Section 12.1.

All summary analyses, including efficacy and safety analyses, will be performed for all patients enrolled in the study who receive any amount of study drug (necitumumab and abemaciclib).

Minor changes or clarifications to any statistical analyses described in this protocol may be presented in the final statistical analysis plan (SAP) for this study.

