### **12.2.6. Primary Outcome and Methodology**

Please refer to Section [12.1](#) for details of the primary analysis.

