5.6. Efficacy Analyses

Efficacy analyses will be performed for the evaluable population. For all time-to-event variables (OS and PFS), the Kaplan-Meier product limit method will be used to estimate the survival curve as well as survival rates at various time points (3-month, 6-month, and 1-year). A 2-sided, 95% confidence interval (CI) for median PFS, median OS, and survival rate at time point will be computed by the Brookmeyer and Crowley method.

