5.6.1. Primary Efficacy Endpoint

The primary endpoint for Part B is the PFS rate at 3 months. Progression-free survival rate at 3 months is defined as the rate of PFS at 3 months from the date of first dose of study drug and is determined using the distribution of overall PFS times. The PFS rate at 3 months is estimated using the Kaplan-Meier method.

Progression-free survival is defined as the time from the date of first dose of study drug until first observation of objective (radiographically documented) PD as defined by Response Evaluation Criteria In Solid Tumors Version 1.1 (RECIST 1.1) or death from any cause, whichever comes first. The censoring is taken in the following order:

- If a patient does not have an adequate baseline radiological tumor assessment, then the PFS time will be censored at the date of first study drug, regardless of whether or not objectively determined disease progression or death has been observed for the patient; otherwise,
- If a patient is not known to have died or have objective progression as of the data inclusion cutoff date for the analysis, the PFS time will be censored at the last adequate objective progression-free disease assessment date.

Adequate radiological tumor assessment refers to an assessment with 1 of the following responses: complete response (CR), partial response (PR), stable disease (SD), or PD. If a tumor assessment was done on multiple days, the earliest date for that visit will be used if overall response is PD, and the last date will be used otherwise (censor).

Progression-free survival sensitivity analysis will be performed. The censoring rules for PFS sensitivity analysis are listed in [Table JFCU.5.1](#).

Table JFCU.5.1. Rules for Determining Date of Progression or Censor for PFS Sensitivity Analysis

Situation	Event / Censor	Date of Event or Censor
Tumor progression or death	Event	Earliest date of PD or death
No tumor progression and no death	Censored	Date of last adequate radiological assessment or date of first dose (whichever is later)
unless		
No baseline radiological tumor assessment available	Censored	Date of first dose
No adequate postbaseline radiological tumor assessment available and death reported after 2 scan intervals following first dose	Censored	Date of first dose

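### The SAP names no Part B evaluable set for the primary test: section 5.6 uses an evaluable population with no Part or dose limit, and the planned total of 68 does not fit the stated Part A/Part B overlap

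*SAP*

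**What the plan says.** SAP 5.2 lists three populations. The only one called evaluable is "all patients who have received at least 1 dose each of necitumumab and abemaciclib and have had a complete radiographic assessment at baseline". It mentions neither Part nor dose. SAP 5.6 then states: "Efficacy analyses will be performed for the evaluable population". SAP 5.6.1 opens with "The primary endpoint for Part B is the PFS rate at 3 months" but names no analysis set. SAP 5.6.2.1 takes all evaluable patients as the ORR denominator, and SAP 5.6.2.2 uses the same one for DCR.

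SAP 5.1 and protocol 12.1 define a different set for Part B: "An evaluable patient for Part B will include any patient enrolled in Part A and treated at the recommended doses of necitumumab and abemaciclib". Further patients are entered to Part B only, for a total of 50, and "these additional patients entered must meet the following criteria": at least one dose of each drug and a complete baseline radiographic assessment. The hypotheses (50% against 65%), the 60% rule, alpha 0.10 and power 81% are all stated for these 50. Protocol 12.2.1 says "The primary analysis will be as described in Section 12.1", and protocol 12.2.6 also refers back to 12.1 "for details of the primary analysis".

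On numbers, SAP 5.1 and protocol 12.1 give about 68 evaluable patients for either Part, up to 18 in Part A (3 to 6 per cohort) and 50 in Part B. They also say that squamous and nonsquamous Part A patients treated at the recommended abemaciclib dose "will also be part of the Part B portion of the trial".

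**The concern.** The study has one formal hypothesis test. The section that assigns the efficacy analysis set should name the set for which the cut-off, alpha and power were worked out. A programmer working from SAP 5.2 and 5.6 would find one evaluable population and could include Part A patients treated at doses not taken into Part B. A primary result close to the cut-off could then turn on those patients. For ORR and DCR the wording gives that pooled set directly, although the Part B objectives in SAP 4.2 are framed at the recommended dose.

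The head count raises a related question. The total of 68 equals 18 + 50 with nobody counted twice, yet the same paragraph says some patients belong to both Parts. Either the total is too high, or the Part B set is larger than the 50 for which the rule was computed.

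**Working it through.** **Inputs** (SAP 5.1 and protocol 12.1): N = 50, null rate 0.50, alternative 0.65, reject if at least 60% are progression-free at 3 months; three Part A cohorts of 3 to 6, at most 18.

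**The plan's own figures.** Cut-off k = 0.60 × 50 = 30. With X the number progression-free, exact binomial:
- alpha = P(X ≥ 30 | 50, 0.50) = 0.101
- power = P(X ≥ 30 | 50, 0.65) = 0.814

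Both agree with the stated 10% and 81%. These and all later figures treat 3-month status as known for every patient; the SAP will estimate the rate by Kaplan-Meier.

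**Pooling the other dose cohorts.** If one or two cohorts other than the recommended one were treated, that adds 3 to 12 patients (2 × 6 = 12). The documents state the 60% rule only for 50. Extending it to larger N as k = ceil(0.6N) is my assumption, as is a common true rate at all doses. The last two columns give the chance that the 5.1 set and the pooled set lead to different decisions.

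| Other-dose patients | N | k | alpha | power | differ at 50% | differ at 65% |
|---|---|---|---|---|---|---|
| 0 | 50 | 30 | 0.101 | 81.4% | – | – |
| 3 | 53 | 32 | 0.084 | 80.3% | 3.2% | 4.8% |
| 6 | 56 | 34 | 0.070 | 79.3% | 4.6% | 7.1% |
| 12 | 62 | 38 | 0.049 | 77.4% | 6.5% | 10.4% |

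The disagreement is P(x ≥ 30 and x + y < k) + P(x < 30 and x + y ≥ k), with x ~ Bin(50, p) and y ~ Bin(m, p), where m is the number of other-dose patients. For m = 12 it is 0.0586 + 0.0062 = 0.0648 at p = 0.50, and 0.0722 + 0.0320 = 0.1042 at p = 0.65.

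At the boundary with m = 12, 30/50 rejects under SAP 5.1 but in the pooled set needs 38 − 30 = 8 of the 12. A result of 29/50 fails under SAP 5.1 but would reject if 38 − 29 = 9 of the 12 were progression-free.

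**The total.** There are two readings of the 50.
- *The 50 includes recommended-dose Part A patients.* The total is 50 plus the other-dose Part A patients, at most 50 + 12 = 62 (equivalently 18 + 50 − 6). This assumes planned cohort sizes and that the whole recommended-dose cohort carries over. Each such patient who does not carry over adds one. That could happen with NSCLC not otherwise specified, which SAP 5.5.2 lists apart from squamous and nonsquamous. The total reaches 68 only if none of six carries over.
- *The 50 are newly entered.* Then 18 + 50 = 68 stands, but with 3 to 6 carried over Part B has 53 to 56 patients:

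| N | k | alpha | power |
|---|---|---|---|
| 53 | 32 | 0.084 | 80.3% |
| 54 | 33 | 0.067 | 77.3% |
| 55 | 33 | 0.089 | 82.1% |
| 56 | 34 | 0.070 | 79.3% |

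**The case against.** The best reply is that the documents already restrict the primary test. SAP 5.6.1 ties the endpoint to Part B. Protocol 6.2 and SAP 4.2 place the Part B efficacy objectives at the recommended dose. SAP 5.10, on the possible interim look at the 3-month PFS rate in nonsquamous patients, counts Part A patients only at the recommended abemaciclib dose. The protocol sends the reader to 12.1 for the primary analysis. This stands. A reader might infer that the SAP plans to pool dose cohorts in the primary test, and the documents do not support that. What remains is that the intended set is never named, while the section that assigns the efficacy set points to another one. The general SAP 5.2 set also has a proper use, the Part A ORR objective.

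A reader might also infer that pooling inflates the type I error. At a common rate alpha falls. Of the 6.5% disagreement at the null with 12 other-dose patients, only 0.6 points are extra rejections. Larger effects need other-dose rates that the documents do not give. Twelve is the top of the planned range but not a strict cap: protocol 8.1 and 9.3.2.1 replace some Part A patients, who could still meet SAP 5.2.

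SAP 5.1 applies the two evaluability criteria only to the newly entered patients, while SAP 5.2 applies them to all. In practice this matters little, because recommended-dose Part A patients have received both drugs and baseline tumour measurement is required of everyone.

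Finally, 68 need not be an arithmetic slip. The synopsis lists 3 to 18 and 50 as separate enrolment counts, and the synopsis and protocol 8.1 speak of approximately 70 patients. Both fit 50 new patients, in which case 68 is right. The words approximately and up to also soften the figures. But on that reading the Part B set is no longer 50, so the text still needs reconciling. The total enters no alpha or power calculation.

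**Conclusion.** The point holds as a conflict between two definitions of evaluable and between stated head counts. It should be fixed, but it is not a flaw in the design. For the primary test the fault is an unnamed analysis set whose intended content is clear; for ORR and DCR the wording does pool dose cohorts.

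If the pooled set were used for the primary test, power would fall by about 1 to 4 points and alpha to between 0.084 and 0.049. The decision would differ in 3.2% to 6.5% of trials at a true rate of 50% and in 4.8% to 10.4% at 65%. These figures assume 3 to 12 other-dose patients, a common rate, the extended 60% rule and known 3-month status.

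On the total, the documents do not settle which reading is meant. It is either at most about 62, or 68 with 53 to 56 in Part B, where the 60% rule has alpha 0.067 to 0.089 and power 77% to 82%. Protocol 8.2 calls the outcome hypothesis generating only, which limits the consequence. N = 50, the cut-off of 30 and the 81% power are sound for the set described in SAP 5.1.

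**What to change.** 1. In SAP 5.2, add a Part B evaluable population: recommended-dose Part A patients plus patients entered to Part B, with at least one dose of each drug and a complete baseline radiographic assessment required of both groups.
2. Name that population in SAP 5.6, 5.6.1, 5.6.2.1 and 5.6.2.2 for the Part B analyses, and report Part A ORR by dose cohort.
3. In SAP 5.1 and protocol 12.1, state whether the 50 includes recommended-dose Part A patients and whether all histologies carry over.
   - If it does include them, restate the total as 50 plus the other-dose Part A patients (up to about 62), and align the approximate 70 in the synopsis and protocol 8.1.
   - If 50 new patients are meant, keep 68 and restate the cut-off, alpha and power for 53 to 56.

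The cost is wording in the SAP and protocol, plus a short recalculation if the second option is chosen. Neither option adds patients beyond the numbers already planned, or any visits or time.

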5.3. Handling of Dropouts or Missing Data

Dates missing the day or both the day and month of the year will adhere to the following conventions:

- The missing day of onset of an adverse event or start date of a concurrent therapy will be set to:
 - first day of the month that the event occurred, if the onset yyyy-mm is after the yyyy-mm of first study treatment
 - the day of the first study treatment, if the onset yyyy-mm is the same as yyyy-mm of the first study treatment
 - the date of informed consent, if the onset yyyy-mm is before the yyyy-mm of the first treatment.

- The missing day of resolution of an adverse event or end date of a concurrent therapy will be set to:
 - the last day of the month of the occurrence. If the patient died in the same month, then set the imputed date as the death date.
- If the onset date of an adverse event or start date of a concurrent therapy is missing both the day and month, the onset date will be set to:
 - 01 January of the year of onset, if the onset year is after the year of the first study treatment
 - the date of the first treatment, if the onset year is the same as the year of the first study treatment
 - the date of informed consent, if the onset year is before the year of the first treatment
- If the resolution date of an adverse event or end date of a concurrent therapy is missing both the day and month, the date will be set to:
 - 31 December of the year of occurrence. If the patient died in the same year, then set the imputed date as the death date
- If date is completely missing, then no imputation will be done and the event will be considered as treatment emergent unless the end date rules out the possibility.

For initial diagnosis date, birthday, and death date, the following conventions will be used for imputing partial dates:

- If only the day of the month is missing, the 15th of the month will be used to replace the missing day.
- If both the day and the month are missing, “Jul 1” will be used to replace the missing information.

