**Clinical Protocol Synopsis: Study I4X-MC-JFCU**

Name of Investigational Product: Necitumumab (LY3012211) and Abemaciclib (LY2835219)	
Title of Study: A Single-Arm, Multicenter, Phase 1b Study with an Expansion Cohort to Evaluate Safety and Efficacy of Necitumumab in Combination with Abemaciclib in Treatment of Patients with Stage IV Non-Small Cell Lung Cancer (NSCLC)	
Number of Planned Patients: Part A Enrolled: 3 to 18 Part B (Expansion Cohort) Enrolled: 50	Phase of Development: 1b

Length of Study: approximately 21 months  Planned first patient visit: 08 Sep 2015  Planned last patient visit: 19 Jun 2017  Planned interim analyses: first 15 evaluable patients in Part B portion of the study who have completed 2 cycles of study treatment (or otherwise discontinued study treatment) will be analyzed for safety. Interim analyses for efficacy may be performed as needed to aid in the planning of future trials. Patients with squamous and nonsquamous NSCLC who received the recommended abemaciclib dose for Part B in Part A will be taken into account for the interim analyses.
	

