5.6.2.3. Overall Survival

Overall survival duration is measured from the date of first dose of study drug to the date of death from any cause. For each patient who is not known to have died as of the data-inclusion cut-off date for a particular analysis, OS will be censored for that analysis at the date of last contact prior to the data inclusion cutoff date (contacts considered in the determination of last contact date include adverse event date, lesion assessment date, visit date, and last known alive date).

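### SAP 5.3 imputes partial death dates without bounds, so a death known only by year can be dated before first dose, before a documented progression, or after the planned end of the study

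*SAP*

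**What the plan says.** SAP 5.3 puts death dates under one convention with two dates that precede the trial: "For initial diagnosis date, birthday, and death date, the following conventions will be used for imputing partial dates". The two rules are "If only the day of the month is missing, the 15th of the month will be used to replace the missing day" and "If both the day and the month are missing, “Jul 1” will be used to replace the missing information". Neither refers to first dose, to when the patient was last known alive, or to the data cutoff.

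The same section does limit adverse-event and concurrent-therapy dates. A start date with the day missing becomes "the day of the first study treatment, if the onset yyyy-mm is the same as yyyy-mm of the first study treatment". For an end date it adds: "If the patient died in the same month, then set the imputed date as the death date".

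SAP 5.2 computes time to event as event date minus first-dose date plus 1, with no minimum. SAP 5.6.1 takes the earlier of radiographic progression and death as the PFS event. SAP 5.6.2.3 measures OS from first dose to death and, for censoring, says "contacts considered in the determination of last contact date include adverse event date, lesion assessment date, visit date, and last known alive date". The protocol synopsis gives the calendar: "Planned first patient visit: 08 Sep 2015" and "Planned last patient visit: 19 Jun 2017". No rule in the protocol's endpoint definitions (10.1.3, 10.1.4) overrides the SAP convention.

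**The concern.** A mid-period date is a reasonable guess for a birthday or an old diagnosis. A death in this trial can only fall after the patient was last known alive and before it was reported, and the rule ignores both limits. The study opens in September of one year and is planned to close in June two calendar years later, so 1 July lies outside the study period in both 2015 and 2017 and in the middle of planned accrual in 2016.

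Death is an event in the primary endpoint and defines OS. A date imputed too early gives a zero or negative time, or replaces a real progression date. A date imputed too late can turn an early death into a 3-month success. The date also feeds the split of deaths into on therapy, within 30 days and later (SAP 5.7.3), and it limits imputed adverse-event end dates. If the rule is left alone, impossible dates would be repaired case by case in an open-label, single-arm trial with outcomes visible.

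**Working it through.** **Inputs.** First visit 8 Sep 2015 and last visit 19 Jun 2017, both planned (protocol synopsis). Time = event − first dose + 1, and 30.4375 days per month, so 3 months = 91.3125 days (SAP 5.2). Design: 50 evaluable patients, success at 60% or more (30 of 50), 50% against 65% (SAP 5.1). The data cutoff is undated, so 19 Jun 2017 stands in for it.

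**The plan's own figure.** Exact binomial with 30 or more of 50: alpha = P(X ≥ 30 | 0.50) = 0.1013 and power = P(X ≥ 30 | 0.65) = 0.8139. These match the stated 10% and 81%.

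**Year-only deaths (1 July).**
1. 2015: 1 Jul to 8 Sep is 69 days. Even the earliest possible patient gets −69 + 1 = day −68, and later patients get lower values.
2. 2016: the time is zero or negative for anyone first dosed after 1 Jul 2016. First dose 1 Aug 2016 gives −31 + 1 = day −30; if the true death was 1 Dec 2016, the true time is day 123.
3. 2016 with documented progression: first dose 1 Jun 2016, progression 20 Oct 2016 (day 142), death later in 2016. The imputed death is day 31 and comes first, so a 3-month success becomes a failure.
4. 2017: 1 Jul is 12 days after 19 Jun. First dose 16 Jan 2017 with true death 1 Mar 2017 is 44 + 1 = day 45; imputed, it is 166 + 1 = day 167, so a 3-month failure becomes a success. A cap at 19 Jun alone still gives day 155.

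**Day-only deaths (the 15th).** The date precedes first dose only if the patient died in the month of first dose and was dosed on the 16th or later. First dose 22 Mar 2016 with death 30 Mar 2016 (day 9) becomes −7 + 1 = day −6. The date also precedes a known contact when the patient was seen alive after the 15th of the month of death. At the planned end, 15 Jun 2017 is 4 days before 19 Jun, so this rule does not overshoot.

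**How often, given a partial date.** An illustrative simulation took first dose as uniform from 8 Sep 2015 to 19 Jan 2017 (five months before the planned last visit). It used exponential survival with assumed medians of 6, 9 and 12 months, deaths up to 19 Jun 2017, and death as the PFS event. The ranges run across the three medians.

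| Share of deaths with that type of partial date | Year only | Day missing |
|---|---|---|
| Dated before first dose | 16–20% | 1.6–2.1% |
| Dated after 19 Jun 2017 | 30–36% | 0% |
| 3-month status changed | 22–25% | 2.4–2.8% |

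**Effect of one changed status.** With 50 evaluable patients and no censoring before 3 months, one patient is 1/50 = 2 percentage points. At the 30-of-50 boundary, one false success acts like a threshold of 29 (alpha 0.161, power 0.881), and one false failure acts like a threshold of 31 (alpha 0.059, power 0.726). These figures are conditional on such an error occurring; they are not expected operating characteristics.

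**The case against.** The strongest case against is rarity. Patients attend on Days 1 and 8 of each 21-day cycle, have a 30-day follow-up visit and 6-weekly scans until progression or new therapy, and are then contacted every 3 months (protocol Attachment 1). An unknown month of death inside the 3-month window is hard to picture for a patient under follow-up. A misdated death also leaves PFS untouched if progression came first, unless the imputed date precedes the progression. The simulated status changes ignore progression and so are only a guide. The sensitivity analysis in Table JFCU.5.1 censors many deaths pushed late, because it discounts a death that follows two or more scan intervals (90 days) without an adequate scan. The protocol itself treats the outcome as hypothesis generating (8.2). All of this stands and limits the expected impact. It does not make the rule correct: the primary analysis has no such protection, and the sensitivity table still takes the earliest of progression and death, so early imputed dates pass through.

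Three stronger readings are tempting, and the documents do not support them.
- **A 2017 death dated after the cutoff becomes censored.** SAP 5.6.1 and 5.6.2.3 censor only patients without a known death. A death reported before the cutoff is known, whatever date is imputed; the SAP just does not say how a date past the cutoff is handled.
- **Partial dates are likely because vital status may come from public sources.** Protocol 7.3.4 allows such searches for patients lost to follow-up and says nothing about how complete the dates will be.
- **Imputed adverse-event end dates extend OS censoring by many months.** SAP 5.6.2.3 does not say which adverse-event date counts or whether imputed dates are used, and it limits contact to before the cutoff. This is an ambiguity to close; its size cannot be stated.

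**Conclusion.** The point holds as a defect in a stated rule. Applied as written, it gives impossible times for every year-only 2015 death and for year-only 2016 deaths in patients first dosed after 1 July 2016. It can override a documented progression, and it leaves year-only 2017 deaths with no defined handling. Most of the harm comes from the 1 July rule; the 15th rule contributes little.

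The size is per affected patient: an impossible or materially wrong PFS or OS time and, where 3-month status changes, 1 of 50. How many patients would be affected is unknown. No frequency is stated, and the follow-up schedule suggests few. The conclusion rests on the planned dates. If the actual cutoff fell on or after 1 July 2017, the 12-day overshoot would vanish, but the 2015 and 2016 failures would remain. The design is not in question.

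**What to change.** Take death out of the shared convention in SAP 5.3 and give it its own rule:
- Set the imputed death date to the later of (a) the 15th or 1 July and (b) the day after the last known-alive date, the latter taken from observed, non-imputed dates.
- Keep the result within the known month or year.
- Cap it at the earlier of the date the death was reported and the data cutoff.

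In SAP 5.6.2.3, state that last contact for OS censoring uses observed dates only.

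Checked on the examples above: the patient with progression on 20 Oct 2016 has an imputed death no earlier than 21 Oct, so progression at day 142 stays the event. The patient dosed on 22 Mar 2016 gets 23 Mar (day 2) or later. For the death on 1 Mar 2017, if it was reported on, say, 10 Mar 2017 (an assumed date), the cap gives 44 + 9 + 1 = day 54, and the 3-month failure is kept. A limit at first dose and cutoff alone would not achieve this. The report-date cap helps only when the death is reported promptly, so a sensitivity analysis that varies any imputed death date within its bounds is worth adding.

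The cost is a few SAP sentences and minor programming, best done before the analysis. Sample size, alpha and power do not change.
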